## 6.2 **Study rationale**

GS-248 is intended to be used for the prevention and treatment of DUs in patients with SSc. Current oral therapies for DUs have limited efficacy, and there is a high medical need for new therapeutic alternatives.

The aim of the present project is to achieve an anti-inflammatory effect by reducing production of the proinflammatory mediator PGE2 and concomitantly, by substrate shunting, to elicit a vasodilatory and platelet inhibitory effect by increased PGI2 production.

The study will collect information about pharmacokinetics (PK), safety and tolerability following a single dose of GS-248 in two different oral solid formulations in capsules to healthy subjects.

The rationale for the study design is outlined in Section 8.2.

### 6.3 Risk/benefit assessment

The healthy volunteers in this study will, except for thorough health examinations, have no medical benefit from participation and their safety and wellbeing are of utmost importance. The FIH study with GS-248, in which the SAD part with doses of 1-300 mg is finalised and did not reveal any noteworthy safety or tolerability findings at any dose level. The current study concerns a single dose of 120 mg in two different formulations, which is well beneath the maximum dose level studied in the FIH study. Adverse drug reactions (ADRs) are therefore not expected.

In a pre-clinical study, pronounced and serious effects on the liver and biliary system were noted in dogs at the highest dose in the 28-day toxicity study. However, no findings that were considered to constitute an adverse effect were noted at the intermediate dose level, primarily based on the total lack of treatment-related histopathological findings at this dose level, and the NOAEL in this study was therefore set at 20 mg/kg. The liver biomarkers will be closely monitored during the present study.

Subjects will remain in the research clinic for approximately 24 h after the single dose and will be closely monitored by medical staff. In addition, subjects will return to the clinic at approximately 48 h post dose for safety check-up.

Overdosing is not likely to occur since all IMP will be administered by site personnel under medical surveillance. In cases of accidental overdose, standard supportive measures should be adopted as required. For further information regarding overdosing, refer to Section 11.4.1.17.

The Principal Investigator at the research clinic will ascertain that adequate facilities and procedures are available to handle emergency situations should they occur during the study. The medical staff at CTC have extensive experience from early Phase I and FIH studies and there are adequate procedures in place to handle unexpected and expected adverse reactions in the study subjects. CTC has been regularly inspected by the Swedish Medical Products Agency (MPA) and is authorised to conduct early phase studies.

Besides the risks related to the IMP as described above, there may also be risks related to the medical devices used in the study, *e.g.*, indwelling venous catheters. However, these are devices that are used in routine medical care and the risk associated with their use is considered low and ethically justifiable. Study specific evaluations and sampling procedures, like blood-pressure measurements using a blood pressure cuff and frequent blood-sampling, may cause transient discomfort but the risk is deemed to be low and ethically justifiable.

Overall, the combined safety data from the pre-clinical studies and the FIH study have not revealed any safety issues that would outweigh the expected benefits of the study. While keeping the above-mentioned risk factors at a minimum level in order to not expose the subjects participating in the study for risks that would not be ethically justifiable, it is concluded that the planned study assessments are considered sufficient to meet the scientific and medical goals for the study. It is therefore concluded that the potential benefits from the study will outweigh the potential risks for the treated subjects.

More detailed information about the known and expected benefits and risks and reasonably expected ADRs of GS-248 is found in the current version of the IB.

## 7 STUDY OBJECTIVES AND ENDPOINTS

### 7.1 Primary objective

- To evaluate the PK of two different solid formulations of oral GS-248 in healthy subjects.
- To evaluate the effect of food on the PK of one of the two formulations of oral GS-248.

#### 7.1.1 Primary endpoints

- The PK parameters of a single dose of two different formulations of GS 248 in fasting conditions. The PK parameters to be assessed include, but are not limited to, maximum plasma concentration ( $C_{max}$ ), time to  $C_{max}$  ( $T_{max}$ ), area under the curve from timepoint 0 to the last measured timepoint ( $AUC_{0-last}$ ), AUC from timepoint 0 to infinity ( $AUC_{0-inf}$ ), plasma half-life associated with the terminal elimination phase ( $T_{1/2(z)}$ ), volume of distribution associated with the terminal elimination phase following non intravenous administration ( $V_z/F$ ), and total clearance of the drug from plasma following non-intravenous administration ( $CL/F$ ). The relative bioavailability of GS-248 after a single dose of Formulation A versus Formulation B, and of one of the two formulations in fed versus fasting conditions.
- The PK parameters of a single dose of one of the two formulations of GS-248 in fed conditions.

### 7.2 Secondary objective

- To evaluate the safety and tolerability of two different solid formulations of oral GS-248 in healthy subjects.
- To evaluate the safety and tolerability of one of the two formulations of oral GS-248 given after a standardised high-fat high-calorie breakfast.

#### 7.2.1 Secondary endpoints

- Frequency, intensity and seriousness of AEs.
- Clinically significant changes in:
  - Physical examination
  - Vital signs
  - Body temperature
  - Resting 12-lead ECG
  - Safety laboratory parameters

## 8 STUDY DESIGN

[figure not shown]
### 8.1 Overall study design and schedule of events

This is a Phase I, open, one-sequence, three-period study in healthy volunteers to evaluate the PK, safety and tolerability of two formulations of GS-248. The study is divided in two parts. Part I will evaluate PK, safety and tolerability of a single oral dose of two different formulations of GS-248 in fasting conditions (Section 8.1.1). Part II will evaluate PK, safety and tolerability of one of the two different formulations of GS-248 in fed conditions (Section 8.1.2).

Subjects are expected to participate in both Part I and Part II and will come to the clinic for a total of 7 visits. Screening (Visit 1) will take place from Day -28 to Day -1 and will include an eligibility check and a general health assessment, see Table 8.1-1 for details. Each subject is expected to participate in the study for approximately 8 weeks including a screening period of up to 4 weeks.

An overview of the study design is shown in Figure 8.1-1.

Figure 8.1-1 Study flow chart

#### 8.1.1 Part I: Two formulations of GS-248 in fasting conditions

In Part I of the study, a single oral dose of GS-248 in two different solid formulations will be administered to 14 healthy subjects. All subjects will first receive Formulation A (a lipid-based formulation in a capsule) and then Formulation B (a dry powder in a capsule, see Section 10.1). A wash-out period of at least 4 days will be applied between the IMP administrations. Both doses contain 120 mg GS-248. The rationale for the dose is detailed in Section 8.3.

For Part I, subjects will come to the clinic for 4 visits. At Visit 2, subjects will be admitted to the clinic on the afternoon/evening of Day -1 and will remain at the clinic until Day 2 (24 h post dose) for single dose administration of Formulation A and PK and safety assessments. The subjects must fast for at least 10 hours before the anticipated dosing time on Day 1. Water, but no other drinks, is allowed as desired except for 1 h before and 1 h after dosing. The subjects will be carefully monitored by clinical staff during and after dosing. Vital signs and ECG will be checked at regular intervals as detailed in Table 8.1-2. The subjects will return to the clinic on Day 3 (Visit 3) at 48 h post dose for PK blood sampling and safety assessments, as outlined in Table 8.1-1. Safety assessments include AE reporting, physical

examination, ECG, vital signs, body temperature, and blood sampling for analysis of safety laboratory parameters.

Visit 4 will be similar to Visit 2, at which subjects will stay overnight at the clinic from Day -1 to Day 2 for single dose administration of Formulation B and PK blood sampling and safety assessments. Visit 5 will be similar to Visit 3, at which subjects return to the clinic on Day 3 for PK blood sampling and safety assessments.

The schedule of events for Part I is shown in Table 8.1-1 and detailed for visit 2-7 in Table 8.1-2.

Study assessments are described in Section 11.

### 8.1.2 ***Part II: Food interaction***

After evaluation of the PK profiles of Formulation A and B in Part I of the study, one formulation will be selected to be given following intake of a standardised breakfast in Part II of the study. In this part, any potential food interaction with GS-248 will be investigated.

After evaluation of the PK results from Part I, subjects will return to the clinic for a second dose of the selected formulation (Visit 6, similar to Visit 2), yet this time in fed conditions. The assessments during fed conditions will be the same as during fasting conditions (see Section 8.1.1), except for the fact that the subjects will consume a high-fat high-calorie breakfast 30 minutes prior to IMP administration as detailed in Section 10.5.

At 48 h post dose, subjects will return to the clinic for PK blood sampling and final end-of-study safety assessments (Visit 7).

The schedule of events for Part II is shown in Table 8.1-1 and detailed for visit 2-7 in Table 8.1-2.

Study assessments are described in Section 11.

Table 8.1-1 Schedule of events

Visit	Refer to CSP section	Screening	Part I						Part II	
		Visit 1 Day -28 to -1	Formulation A		Wash-out >4 days	Formulation B		Wash-out and PK calc >14 days	Formulation A or B fed	
			Visit 2 	Visit 3 		Visit 4 	Visit 5 		Visit 6 	Visit 7 
			In-clinic			In-clinic			In-clinic	
Assessment		Day -1 to 2	Day 3	Day -1 to 2	Day 3	Day -1 to 2	Day 3			
Informed Consent	14.3	X								
Inclusion/exclusion criteria	9.4, 9.5	X	X 							
Demographics	11.2.3	X								
Medical/surgical history	11.2.5	X								
HIV, hepatitis B and C	11.2.7	X								
Alcohol breath test	11.2.10	X	X		X			X		
Weight/height (BMI)	11.2.4	X							X 	
Pregnancy Test 	11.2.8	X	X		X			X	X	
Urine Drug Screen 	11.2.9	X 	X	X	X	X		X	X	
Physical Examination	11.4.2	X	X 		X 			X 	X	
Laboratory Safety	11.4.6	X	X	X	X	X		X	X	
Vital Signs	11.4.3	X	X	X	X	X		X	X	
Body temperature	11.4.4		X	X	X	X		X	X	
12-lead ECG	11.4.5	X	X	X	X	X		X	X	
Baseline symptoms	11.2.11	X	X							
IMP administration	10.5		X		X			X		
PK blood sampling 	11.3.1		X	X	X	X		X	X	
Breakfast (standardised)	10.5							X		
Other meals (standardised) 			X		X			X		
Prior/concomitant med.	11.2.6		----- X -----							
AEs 	11.4.1		----- X -----							

CSP = Clinical study protocol, HIV= human immunodeficiency virus, BMI = body mass index

1. Details in separate schedule (Table 8.1-2).
2. Eligibility check before IMP administration.
3. Only weight assessments.
4. Females only. At screening visit: plasma/serum tests; at other visits: urine test.
5. Drug tests may also be performed at 1 to 2 additional random occasions during the study.
6. Brief physical examination only
7. Timing of PK blood sampling is outlined in Table 8.1-2.
8. At visit 2, 4 and 6, standardised meals are served as outlined in Table 8.1-2.
9. From first administration of IMP.

Table 8.1-2 Detailed schedule of events for visit 2-7

Visit	Refer to CSP section	Visit 2, 4, 6															Visit 3, 5, 7
		Day -1	Day 1														Day 2
Assessment	Time 		Pre-dose	00:00	00:15	00:30	01:00	01:30	02:00	03:00	04:00	06:00	08:00	12:00	16:00	24:00	48:00
Inclusion/exclusion criteria	9.4, 9.5		X 														
Alcohol breath test	11.2.10	X															
Weight/height (BMI)	11.2.4																X 
Pregnancy Test 	11.2.8	X															X 
Urine Drug Screen 	11.2.9	X															X
Physical Examination	11.4.2	X 															X 
Laboratory Safety	11.4.6	X															X
Vital Signs	11.4.3	X							X				X			X	X
Body temperature	11.4.4	X							X				X			X	X
12-lead ECG	11.4.5	X							X				X			X	X
Baseline symptoms	11.2.11	X 	X 														
IMP administration	10.5			X													
PK blood sampling 	11.3.1		X		X	X	X	X	X	X	X	X	X	X	X	X	X
Breakfast (standardised) 	10.5		X 														
Other meals (standardised) 			X														
Prior/concomitant med.	11.2.6	----- X -----															
AEs	11.4.1	----- X -----															

1. Time is denoted in hh:mm. Time points reflect time in hours and minutes after IMP administration.

2. Only at Visit 2.
3. Only weight assessments.
4. Only at Visit 7 (end-of-study visit) or after early withdrawal.
5. Females only. Urine test.
6. Drug tests may also be performed at 1 to 2 additional random occasions during the study.
7. Brief physical examination only, may be performed on Day -1 or Day 1 pre-dose.
8. Actual time for PK sampling must not deviate more than  $\pm 10\%$  from the planned time. The pre-dose sample may be taken within 60 minutes prior to dose. Refer to Section 11.3.1 for more information about timing of PK samples.
9. Standardised breakfast only at Visit 6, not at Visit 2 and 4. Breakfast should be served 30 min before IMP administration.
10. Standardised lunch, snack, dinner and evening snack at approximately 4, 7, 9 and 11 hours post breakfast.

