- Caffeine: Consumption of up to 5 cups of coffee (or equivalent) per day will be allowed from 48 h before each visit and during each visit.
- Xanthine or taurine containing products/beverages: Energy drinks (e.g. Red bull) are not allowed during the study from 48 h prior to first IMP administration until the end-of-study visit.
- Nicotine: Smoking or use of nicotine-containing products is not allowed during the study from screening until the end-of-study visit.
- Grapefruit and grapefruit containing products: Consumption of grapefruit and/or grapefruit-containing products, Seville oranges is not allowed during the study from screening until the end-of-study visit.
- Blood donation: The subjects must not donate blood or plasma during the study from first IMP administration until three months after the end-of-study visit.
- Participation in other clinical studies: Study subjects are not allowed to participate in any other interventional clinical study during the study period.
- Sun protection: Protection from the sun is required from day of IMP administration (Day 1) until 48 h post dose (Day 3) in each sequence. Study subjects are required to follow the recommendations given by Centres for Disease Control and Prevention (CDC, see [15]):
  - Stay in the shade, especially during peak hours of 10 AM to 4 PM.
  - Wear clothing that covers arms and legs
  - Use a hat or cap that shades the face, head, ears and neck
  - Wear sunglasses that block both ultraviolet A (UVA) and ultraviolet B (UVB) rays
  - Proper use of a broad-spectrum sunscreen with a sun protection factor (SPF) of 15 or higher.
  - Abstain from use of tanning beds.
- Exercise: Subjects will abstain from strenuous exercise for 72 h before each blood collection for clinical laboratory tests.

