### 17.1 General

Continuous data will be presented in terms of evaluable and missing observations, arithmetic mean, standard deviation (SD), median, minimum and maximum value. In addition, for the parameters AUC and  $C_{max}$  the geometric mean and coefficient of variation (CV) will be presented.

Categorical data will be presented as counts and percentages. When applicable, summary data will be presented by treatment, and by assessment time. Individual subject data will be listed by subject number, treatment, and, where applicable, by assessment time.

All descriptive summaries and statistical analyses will be performed using SAS Version 9.4 or later (SAS Institute, Inc., Cary, NC).

Baseline will be defined as the last data collection point prior to each administration of IMP.

All hypothesis testing will use a significance level of 5%.

No imputation of missing data will be performed.

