### **17.6.3 Vital signs**

Vital signs (systolic/diastolic BP, pulse) will be summarised. Data will be presented with absolute and percent change from baseline at each visit. Clinical evaluation of vital signs will be summarised in frequency tables.

All data will be listed by subject.

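### The last scheduled vital signs, temperature and ECG before each dose are afternoon/evening Day -1 values, so change from baseline at 2, 24 and 48 h includes a time-of-day difference that a Day 1 pre-dose baseline would cheaply reduce

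*Protocol*

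**What the plan says.** **Schedule.** In protocol Table 8.1-2 the rows "Vital Signs 11.4.3 X X X X X" and "Body temperature 11.4.4 X X X X X" each carry five marks, under Day -1, 2 h, 8 h, 24 h and 48 h. The 12-lead ECG row has the same pattern. The pre-dose cell on Day 1 is empty in all three. Footnote 7 gives a Day 1 option for one other row only: "Brief physical examination only, may be performed on Day -1 or Day 1 pre-dose".

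**Clock time.** Section 8.1.1 states that "subjects will be admitted to the clinic on the afternoon/evening of Day -1", and Visits 4 and 6 are described as similar to Visit 2. No clock time for dosing is given. Section 10.5 requires an overnight fast of at least 10 h. Section 9.6.1 places lunch at 4 h and snack, dinner and evening snack at about 7, 9 and 11 h after the dose.

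**Food and caffeine.** Section 9.6.1 says: "Consumption of up to 5 cups of coffee (or equivalent) per day will be allowed from 48 h before each visit and during each visit". In Part I only water is allowed around dosing, with no food until 4 h after it. In Part II a high-fat breakfast starts 30 minutes before the dose (Section 10.5).

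**Baseline and its use.** Protocol 17.1: "Baseline will be defined as the last data collection point prior to each administration of IMP". SAP 5.3 instead takes the latest measurement before the first dose. For vital signs, "Data will be presented with absolute and percent change from baseline at each visit" (protocol 17.6.3); protocol 17.6.4 and SAP 8.4.1.3 plan the same for temperature. For ECG, the text of both documents plans categories and shift tables, while the SAP table shell adds absolute and relative change. Section 9.8.2 has a QTc withdrawal criterion based on change from baseline.

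**The concern.** A within-subject change supports a drug effect only if the two measurements are otherwise taken under comparable conditions. Here most post-dose values appear to be morning values set against an afternoon or evening value from the day before. The study has one sequence, no placebo period and no randomisation, so nothing in the within-period change separates time of day from drug. More subjects would not help, because the difference comes from the schedule. The 2 h point matters most: it lies inside the 1 to 2.5 h range in which the first-in-human study reached maximum concentration (Section 6.1.6), and it is where a haemodynamic or ECG effect would be looked for first.

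**Working it through.** The plan states no figure on this point, so there is none to reproduce. The check is of timing, then of precision.

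**1. Are the empty pre-dose cells real?** The PK row of Table 8.1-2 is marked at pre-dose and at all 13 post-dose times from 15 minutes to 48 h, which confirms the column alignment. The missing pre-dose marks are therefore not an extraction artefact.

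**2. Is dosing in the morning?** This is inferred. A dose at 08:00, for example, puts lunch at 12:00, the snack at 15:00, dinner at 17:00 and the evening snack at 19:00, which fits an overnight fast.

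**3. Clock-time gap.** Assumptions, not in the documents: dose time D between 07:00 and 10:00; Day -1 assessment B between 14:00 and 20:00. Gap at h hours = [(D + h) mod 24] − B.

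| Time point | D = 10, B = 14 | D = 7, B = 20 |
|---|---|---|
| 2 h | 12 − 14 = −2 h | 9 − 20 = −11 h |
| 8 h | 18 − 14 = +4 h | 15 − 20 = −5 h |
| 24 h and 48 h | 10 − 14 = −4 h | 7 − 20 = −13 h |

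The 2, 24 and 48 h values fall earlier in the day than baseline throughout the assumed range; the 8 h value straddles it. These are nominal times. The 10% window in Section 11.1 moves the 2 h value by only 0.2 h but the 48 h value by up to 4.8 h, so at the late edge the smallest 48 h gap becomes −4 + 4.8 = +0.8 h.

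**4. Gap with a Day 1 pre-dose baseline.** If it is taken u hours before the dose, with u from 0 to 1 (the existing pre-dose PK window), it precedes the 2 h value by 2 + u = 2 to 3 h and differs from the nominal 24 and 48 h clock times by 0 to 1 h. At Visit 6, before breakfast starts, u is 0.5 to 1, giving 2.5 to 3 h and 0.5 to 1 h.

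**5. Food and caffeine.**
- Day -1: the fast need not begin until D − 10, that is 21:00 to 00:00, so the baseline need not be fasting. Coffee is allowed.
- 2 h, Part I: at least 10 + 2 = 12 h without food, water only.
- 2 h, Part II: 2.5 h after breakfast began, so fed; drinks limited to water and the breakfast milk.
- 24 h: the last scheduled meal is the evening snack at about 11 h. 48 h: food state unspecified. Coffee is allowed at both, as on Day -1.

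The combined fasting and caffeine contrast is thus documented only at 2 h in Part I.

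**6. Which baseline?** Under protocol 17.1 it is the Day -1 value of each period. Under SAP 5.3 it is the Day -1 value of Visit 2 for all periods. Both are afternoon or evening values.

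**7. Precision of a mean change.** The 95% half-width in units of the SD of change is t(0.975, n−1)/√n: 0.58 at n = 14 and 0.64 at n = 12. An assumed shift of s SDs equals s√n standard errors:

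| s (assumed) | n = 14 | n = 12 |
|---|---|---|
| 0.25 | 0.9 | 0.9 |
| 0.5 | 1.9 | 1.7 |
| 0.75 | 2.8 | 2.6 |
| 1.0 | 3.7 | 3.5 |

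This is a yardstick for reading the tables, not a planned test.

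**The case against.** The strongest reply is that little depends on these tables.

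- The secondary endpoint is clinically significant change, judged by the investigator finding by finding, not by a mean. Safety summaries are descriptive. The p-values in SAP 4.3 concern systemic exposure.
- The ECG analysis in the text is categorical; numeric change appears only in a table shell.
- All three periods share one schedule, so a common shift largely cancels between formulations.
- Measured values are tabulated beside the changes. The 48 h value is roughly clock-matched to the 2 h value and probably low in exposure: Section 8.2 reports no subject above 5% of maximum concentration 48 h after multiple 180 mg doses.

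All of this stands, and it limits the point. It does not repair the within-period change tables, which are the planned presentation for vital signs and temperature. The 48 h comparison is not planned, and food state at 48 h is not specified.

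A reader might infer more than the documents support:

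- **A shift of one sign in every subject and period.** Neither sign nor size can be derived, and the food state at 2 h differs between Part I and Part II.
- **A combined meal and caffeine shift at 24 and 48 h.** Coffee is allowed at those times as on Day -1, and no comparable food contrast is documented.
- **A false-positive rate for safety findings.** This would need assumed shifts and SDs, and a test that nobody plans.
- **Wrong decisions under the QTc criterion.** Nothing shows a shift that is material against its 60 ms threshold.

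**Conclusion.** The point holds as a cheap improvement to secondary safety summaries. The primary PK endpoints are untouched. The descriptive changes from baseline in vital signs and temperature, the numeric ECG change in the SAP shell, and the baseline against which the QTc change criterion would ordinarily be read all carry a time-of-day difference that cannot be separated from a drug effect at 2, 24 and 48 h. At 2 h in Part I a fasting and caffeine difference is added. Under the assumed clock times the mismatch is 2 to 11 h at 2 h and nominally 4 to 13 h at 24 and 48 h.

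This rests on morning dosing, which is inferred, and on assessment soon after an afternoon or evening admission. Footnote 7 supports it only by contrast; the table rows and the admission time are the direct evidence. The effect on the measurements themselves cannot be sized from the documents.

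**What to change.** 1. In Table 8.1-2, at Visits 2, 4 and 6, move the Day -1 vital signs, body temperature and 12-lead ECG to Day 1 pre-dose, within the existing 60-minute pre-dose PK window. At Visit 6, complete them before breakfast starts. Leave safety laboratory samples on Day -1 so that results are available before dosing.
2. Align SAP 5.3 with protocol 17.1 so that each period's own pre-dose value is its baseline. The schedule edit alone is not enough: under the SAP wording, the new values at Visits 4 and 6 would not serve as baseline.
3. Note with the Visit 6 results that a meal difference remains between the pre-breakfast baseline and the 2 h value.

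The number of measurements is unchanged and subjects are already in the unit. The cost is a busier pre-dose hour. Visit 6 is tightest: a 60-minute window less the 30 minutes before dosing taken by breakfast leaves about 30 minutes for the PK sample, ECG and vital signs, including 10 minutes of supine rest. An abnormal admission value would also be seen on the dosing morning rather than the evening before.

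The SAP describes the dosing of 14 subjects in the past tense. If the visits are already complete, step 1 is no longer available. The baseline definitions should still be reconciled, and the change tables should carry a note on the time-of-day difference.

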### 9.6.1 *General restrictions*

- Contraception Requirements:

The male subjects are expected to use condom to prevent pregnancy and drug exposure of a partner and refrain from donating sperm from the date of first dosing until three months after last dosing of the IMP. Female partners of child-bearing potential are expected to use contraceptive methods with a failure rate of < 1% to prevent pregnancy (for details, refer to inclusion criterion No 5) during the same period.

Female subjects of child-bearing potential must use effective contraception (defined in inclusion criterion No 5) or practice abstinence during the study and for 30 days after IMP administration. Female subjects must refrain from donating eggs from the date of dosing until 3 months after dosing with the IMP. Their male partner must agree to use a condom during the same time frame if he has not undergone vasectomy.

- Meals and Dietary Restrictions:

**Part I:** Subjects should be fasting overnight (10 hours) before IMP administration and until 4 hours post dose. IMP will be swallowed together with 240 mL tap water.

**Part II:** IMP will be administered within 30 minutes after intake of a standardised breakfast and swallowed together with 240 mL tap water.

For details on IMP administration in the fasted and fed state, refer to Section 10.5.

**Part I and Part II:** Standardised meals will be served while the study subjects are in the research clinic. Lunch will be served 4 hours post dose. Snack, dinner and evening snack will be served approximately 7, 9 and 11 hours post dose, respectively. Water is allowed ad libitum at the clinic except one hour before dose and one hour after dose on dosing days.

Standardised meals: A menu option (decided by CTC) will be offered while the study subjects are in the research clinic. The meal selection is standardised in the sense that the nutritional content of the meals should be similar at each time point of each treatment day.

- Alcohol: Consumption of alcohol is not allowed within 48 hours prior to the screening visit and prior to and during all subsequent clinic visits, including the end-of-study visit.
- Drugs of abuse: Use of drugs of abuse is not allowed during the study from screening to the end-of-study visit. In addition to the urine drug testing described in Table 8.1-1, additional random testing can be performed at the clinic visits.

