### **Part II - fed conditions**

Following an overnight fast of at least 10 h, subjects will start a high-fat high-calorie breakfast 30 min prior to administration of the IMP (for details on the breakfast, see below). The subjects should eat this meal in 30 min or less, however, the IMP should be administered 30 min after start of the meal. The IMP (3 capsules) will be administered with 240 mL water. No food is allowed for at least 4 h post dose. Water, but no other drinks, is allowed as desired except for 1 h before and 1h after IMP administration (with the exception of the milk that is included in the breakfast, see below).

The high-fat, high-caloric breakfast will consist of the following (or equivalent): 2 eggs fried in butter, 2 strips of bacon, 2 slices of toast with butter, 4 ounces hash brown potatoes (113 g) and 8 ounces (ca 240 mL) milk 3%. Substitutions in this meal can be made as long as the meal provides a similar amount of calories from protein, carbohydrate, and fat and has comparable meal volume and viscosity. The test meal should derive approximately 150, 250, and 500-600 calories from protein, carbohydrate, and fat, respectively.

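### Table 8.1-2 note 10 times the later meals from breakfast, not from dose: it defines no time at Visits 2 and 4 and gives a nominal lunch at 3.5 to 4.0 h post dose at Visit 6

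*Protocol*

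**What the plan says.** The timing of meals after dosing is stated in several places in the protocol.

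- **Table 8.1-2, note 10** (the row for other standardised meals): "Standardised lunch, snack, dinner and evening snack at approximately 4, 7, 9 and 11 hours post breakfast".
- **Table 8.1-1, note 8**, sends staff to that table for all three dosing visits: "At visit 2, 4 and 6, standardised meals are served as outlined in Table 8.1-2".
- **Table 8.1-2, note 9**: "Standardised breakfast only at Visit 6, not at Visit 2 and 4". It continues: "Breakfast should be served 30 min before IMP administration".
- **Section 9.6.1**, under the text that applies to Part I and Part II: "Lunch will be served 4 hours post dose". The rest follows: "Snack, dinner and evening snack will be served approximately 7, 9 and 11 hours post dose, respectively".
- **Section 10.5** prohibits food for at least 4 h after dosing in both the fasting and the fed part. For the fed part it adds: "The subjects should eat this meal in 30 min or less, however, the IMP should be administered 30 min after start of the meal".

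**The concern.** Note 10 and Section 9.6.1 use the same four numbers but count them from different events. Identical numbers with different anchors suggest a drafting slip. The note still matters, because Table 8.1-1 makes Table 8.1-2 the meal schedule for Visits 2, 4 and 6. In the text available, the row for other meals cites no protocol section in either table, whereas the breakfast row cites 10.5. Someone working from the schedule is therefore led to note 10 and not to 9.6.1.

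The food effect is a primary objective. It is estimated by comparing Visit 6 with the same subject's fasting visit on the selected formulation. Section 8.1.2 intends assessments in the two conditions to be the same apart from the breakfast. If lunch came sooner after the dose at Visit 6 than at the fasting visit, that would be a second and unintended difference between the periods. There is a PK sample at 4 h, and a lunch at 3.5 h would precede it in the fed period only. A lunch that complied with note 10 but broke the fast in 10.5 would also leave it unclear whether a protocol deviation had occurred. Deviations judged to affect the analysis remove a subject from the food-interaction PK set (Protocol 17.3.3; SAP 5.2.3), where the aim is at least 12 evaluable subjects out of 14 dosed.

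**Working it through.** The check is clock arithmetic, with the dose at 0 h.

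**Inputs**
- Meal offsets under note 10: 4, 7, 9 and 11 h after breakfast.
- Start of breakfast at Visit 6: 30 min before dosing, so at -0.5 h (note 9; Section 10.5).
- Length of breakfast: m minutes, with m at most 30 (Section 10.5).
- Reference schedule: 4, 7, 9 and 11 h post dose (Section 9.6.1).
- Fast after dosing: at least 4 h (Section 10.5).

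**Visits 2 and 4.** No breakfast is given, so note 10 has no starting point and yields no time.

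**Visit 6, counted from the start of breakfast.** Post-dose time = -0.5 + offset:
- lunch: -0.5 + 4 = 3.5 h
- snack: -0.5 + 7 = 6.5 h
- dinner: -0.5 + 9 = 8.5 h
- evening snack: -0.5 + 11 = 10.5 h

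**Visit 6, counted from the end of breakfast.** The meal ends at -0.5 + m/60 h, so lunch is at 3.5 + m/60 h:

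| Meal length m | Lunch, h post dose |
|---|---|
| 15 min | 3.5 + 0.25 = 3.75 |
| 20 min | 3.5 + 0.33 = 3.83 |
| 30 min | 3.5 + 0.50 = 4.0 |

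With m = 30 the meal ends at the moment of dosing, and note 10 then reproduces the 9.6.1 schedule of 4, 7, 9 and 11 h exactly.

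**Range over both anchors.** Lunch falls at 3.5 to 4.0 h, snack at 6.5 to 7.0 h, dinner at 8.5 to 9.0 h and evening snack at 10.5 to 11.0 h. Each meal is 0 to 0.5 h early against 9.6.1. The nominal lunch time is below 4 h unless the clock runs from the end of a meal that took the full 30 minutes.

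**Cross-check.** Section 9.6.1 describes fed dosing more loosely, as within 30 minutes after breakfast. Counted from the end of the meal, this gives lunch between 4 - 0.5 = 3.5 h and 4 - 0 = 4.0 h, the same range. Dosing 30 min after the end of a 30-minute meal, counted from its start, would give 4 - 1.0 = 3.0 h. That contradicts the dosing time fixed in 10.5 and note 9, so it is not used.

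**The case against.** The strongest reply is that all the instructions can be met at once. Note 10 says *approximately* and gives no tolerance. Lunch at 4 h post dose is 4.0 to 4.5 h after breakfast, depending on the anchor, which fits an approximate 4 h. An approximate time should also give way to an explicit prohibition. This stands: the times above are nominal, and following note 10 does not force a breach of the fast. It does not clear the note, because the limit in 10.5 is a minimum and the note aims at or below it.

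A reader might infer that Part I has no usable meal rule. The documents do not support that. Section 9.6.1 gives a complete post-dose schedule for both parts, and 10.5 repeats the fast for Part I. Only the note fails at Visits 2 and 4.

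A reader might also take note 1 to Table 8.1-2 as a further contradiction: "Time points reflect time in hours and minutes after IMP administration". That note explains the time points in the column headings. It does not govern a footnote that names its own anchor, so nothing here rests on it.

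Finally, safeguards exist. The SAP plans a meals listing (Listing 16.2.14), and the PK set definitions allow subjects with relevant deviations to be excluded. These could help to find and handle an early lunch, but they do not settle which instruction staff should follow.

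**Conclusion.** Note 10 is wrong as written, and the error is minor. It conflicts with 9.6.1, cannot be applied at Visits 2 and 4, and at Visit 6 places lunch nominally 0 to 0.5 h before the fast in 10.5 has ended. The same shift of up to 0.5 h, relative to the fasting reference period, applies to every later meal that day. These figures assume breakfast starts exactly 30 min before dosing and lasts no more than 30 min.

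The problem arises only if staff work from note 10, since 9.6.1 and 10.5 already state the intended rule. It would go too far to infer that the fast was broken or that the food-effect estimate is biased. The documents show neither, and they contain nothing from which an effect on the AUC or Cmax ratio could be computed. Any such effect is probably small. The design itself, a 4 h fast with later meals timed from the dose, is sound.

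**What to change.** In Table 8.1-2, note 10, replace breakfast with dose as the anchor and state that the note applies at Visits 2, 4 and 6. Lunch is then at 4 h post dose and no earlier. Snack, dinner and evening snack are at approximately 7, 9 and 11 h post dose. This matches 9.6.1 and respects 10.5.

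As a separate and optional addition, the note could say that lunch is served after the 4 h PK sample. Neither 9.6.1 nor 10.5 contains that rule. Section 11.1 ranks PK sampling first among the assessments but does not mention meals.

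The cost is the rewording of one table note, with no new procedures and no change to the analysis.
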